9.2.1. Sample Size Assumptions

For the three parameter Emax model, assuming that the sample size is 75, E0 = -0.666 and Emax = 5.258 (estimates based on PHI113633 Emax model), and SD for Hgb change = 1 g/dL (as assumed for study PHI113633 sample size calculation), the following table describes the precision for estimation of target dose (TD) and minimally effective dose (MED) based on different assumptions for the unknown parameter ED50. The relatively low precisions are at least partly due to the fact that the assumed ED50s lie outside the three-times weekly dose range for this study.

Table 4 Precision for Target Dose (TD) and Minimally Effective Dose (MED)

	Sample Size	ED50	Precision (Half-width of 95% CI) for target dose/MED
TD	75	37.28 ¹	2.86
	75	78 ²	5.94
MED	75	37.28 ¹	2.85
	75	78 ²	5.34

- 1. ED50 = 16 mg (assumed ED50 for PHI113633) x 2.33 (theoretical dose ratio).
- 2. ED50 = 33.41 mg (estimated ED50 from PHI113633) x 2.33 (theoretical dose ratio).

For the linear model described in Section 9.4.1.2, assuming the sample size is 75, the following table describes the precision for a range of estimated slopes from 0.03 to 0.07 and different standard deviations for three-times weekly dose (SDx) and Hgb change (SDy). Based on the dose-response curve of GSK study PHI13633 and the assumed theoretical dose ratio of 2.33 between three-times weekly and QD doses, it is estimated that the slope for the linear model with three-times weekly dose as the independent variable is about 0.05. The slopes of 0.03 and 0.07 are also explored as part of the sensitivity analysis.

Table 5 Precision for Linear Regression Slop (Actual distance from slope to limits)

Slope	SDx	SDy	Precision
0.03	9.0	1.0	0.025
0.03	9.0	1.5	0.038
0.03	10.0	1.0	0.022
0.03	10.0	1.5	0.034
0.03	11.0	1.0	0.020
0.03	11.0	1.5	0.031
0.05	9.0	1.0	0.023
0.05	9.0	1.5	0.037
0.05	10.0	1.0	0.020
0.05	10.0	1.5	0.033
0.05	11.0	1.0	0.018
0.05	11.0	1.5	0.030
0.07	9.0	1.0	0.020
0.07	9.0	1.5	0.035
0.07	10.0	1.0	0.017
0.07	10.0	1.5	0.031
0.07	11.0	1.0	0.014
0.07	11.0	1.5	0.027

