9.4.1. Primary Analyses

9.4.1.1. Dose Response Model

The primary endpoint is change in Hgb from baseline at Day 29. To model the dose-response relationship a three-parameter Emax model is planned, where Emax is assumed an appropriate model based on the biology and QD-dose-response modeling completed to date for GSK 1278863.

This model assumes the following form:

$$\Delta Hgb = E0 + \frac{(Emax - E0)}{1 + (\frac{ED50}{dose})} + \in$$

Where:

- \bullet AHgb is the change in Hgb from baseline at Day 29
- E0 is the placebo response
- Emax is the maximum response
- ED50 is the dose that attains the intermediate response, i.e. where (E0+Emax) / 2, is attained

• ε is a random error assumed to be normally distributed with mean zero and constant variance (σ^2)

The observed change in Hgb from baseline at Day 29 will be used as the response variable in the Emax model. Subjects who have a Day 15 Hgb measurement but a missing Day 29 Hgb measurement will be included with a Day 29 value imputed (see Section 9.3.2). Any subject who prematurely discontinues dosing prior to Day 15 will be non-evaluable for the dose-response analysis.

The Emax model will be fitted using Bayesian statistical methods (i.e. a posterior Emax model). Prior distributions for the model parameters have been based on the estimates obtained from GSK study PHI113633. This modeling provides confidence in setting prior distributions for E0, however, there is greater uncertainty in the estimation of Emax and ED50 and this will be explored in sensitivity analyses that will apply alternative (weaker) prior distributions.

Table 6 Prior Distributions for the Primary Model

Emax Model Parameters	Bayesian Priors
E0	~Normal (-0.67, (0.146) ²)
Emax	~Normal (5.26, (1.337) ²)
ED50	~Uniform (10, 120)
Tau (1/σ²)	~Gamma (1,1)

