
The model will be used to make the following inferences to describe the dose response relationship:

- Estimation of the three-times weekly minimally effective dose (MED), defined as the smallest dose achieving a change of -0.5 g/dL over 29 days after being switched from ESA. To estimate this value a variable in the PROC MCMC code will be tracked with the MCMC algorithm and calculated as follows where $\Delta Hgb = -0.5$

Primary Statistical Analyses

$$MED = ED50 \left(\frac{\Delta Hgb - E0}{E_{max} - \Delta Hgb} \right)$$

- Estimation of three-times weekly dose levels from the MED in +0.25 g/dL mean Hgb increments, including estimation of the target dose (TD), defined as the three-times weekly dose of GSK1278863 that achieves a 0 g/dL change over 29 days after being switched from ESA will be made. These variables will be calculated similar to the MED, as shown above, where ΔHgb equals -0.25, 0, 0.25, 0.5, 0.75 and 1.

As well as the dose-response Emax curve, the following figures will be produced:

- A posterior probability distribution of predicted Hgb (g/dL) change over 29 days for each treatment group. Separate variables to estimate the predicted Hgb (g/dL) change at day 29 for doses 0, 10, 15, 25, and 30 will be derived and tracked within the MCMC algorithm. The mean and SD will be calculated for each variable. The dose, along with the mean and SD of its corresponding predicted Hgb change at day 29 will be output into a text file, then R or SAS will be used to produce the plot.
- A predictive posterior probability distribution of Hgb (g/dL) change over 29 days anticipated for a future subject, for each treatment group. The PREDDIST statement will be used in PROC MCMC to predict Hgb change from baseline in future subjects, for each of the studied doses.
- Density plots for each Emax parameter showing the prior and posterior distribution for the primary and sensitivity priors analyses overlaid (Sensitivity priors are described below in Section Sensitivity and Supportive Statistical Analyses.) The sample data generated from the MCMC method will be used to plot the posterior density. R or SAS will then be used to produce this plot for each Emax parameter.

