- For each TIW dose (10mg, 15mg, 25mg, and 30mg), the observed mean Hgb response (Hgb change from baseline) at day 29 can be calculated. Using the observed mean Hgb response values as a bridge, the corresponding QD doses will be estimated using Emax models or a linear model. TIW dose divided by the corresponding QD dose will be used to estimate the dose ratio between them. The TIW doses, the observed mean Hgb responses, and the corresponding estimated QD doses, dose ratios, and the 95% CIs (bootstrap CIs or Bayesian credibility intervals) will be displayed in a table.
- Another way to estimate the dose ratios is to use a selected series of Hgb responses. For each Hgb response value (such as a change of 0.25 g/dL), the corresponding TIW dose and QD dose can be calculated using either an Emax model, or a linear model. The possible Hgb responses choices are: a change of -0.5, -0.25, 0, 0.25, 0.5, 0.75, 1 g/dL between baseline and day 29. The Hgb responses, and the corresponding TIW doses, QD doses, Dose ratios, and their 95% CIs (bootstrap CIs or Bayesian credibility intervals) will be presented in a table.
- In the above two methods, fairly similar dose ratios across the doses indicate the dose ratios is not dose-dependent. Under this assumption, the ratio between the estimated ED50s from the TIW Emax model (this study) and the QD Emax model (GSK study PHI113633) would be equivalent to the dose ratio, as well as the ratio between the estimated slopes from the QD linear model (GSK study PHI113633) and three-times weekly linear model (this study).
- An additional way to explore the dose ratio is to draw a TIW dose vs. QD dose plot using the pair of TIW doses and QD doses obtained from the above methods. The appropriate models to investigate the dose ratio will be fitted based on the plot. If the relationship between the TIW doses and the QD doses is linear, then a linear model $Dose_{TIW} = a + bDose_{QD}$ can be fitted. If the relationship between the TIW and QD doses is generally linear and the magnitude of a dose not deviate from zero in a clinically meaningful way, then it suggests that the dose ratio is not dose dependent. Otherwise if a shows a clinically meaningful difference from 0 or the relationship between the TIW and QD doses is not linear, then it suggests that the dose ratio may be dose dependent. Additional models may be used to further examine how the dose ratio changes when QD dose changes.

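### The MED formula has no floor at zero, so MED draws can be negative doses, and the dose-ratio row at -0.5 g/dL becomes unreliable

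*SAP*

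**What the plan says.** SAP 7.1.2 (Posterior Estimates) gives the MED as "defined as the smallest dose achieving a change of -0.5 g/dL over 29 days". On computation it says: "To estimate this value a variable in the PROC MCMC code will be tracked with the MCMC algorithm". The expression is ED50 x (dHgb - E0)/(Emax - dHgb), with dHgb = -0.5. The target dose (TD) and the other selected doses use the same expression with other values of dHgb.

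Under Model Results Presentation, the planned summaries for MED, TD and the selected doses are the median and the 95% credibility interval. Predictions are made over doses from 0 to 50 mg.

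Under Dose Ratio Estimation, TIW and QD doses are read off at chosen responses and divided: "The possible Hgb responses choices are: a change of -0.5, -0.25, 0, 0.25, 0.5, 0.75, 1 g/dL". Limits for the Bayesian ratios are percentiles of the draw-level values. Similar ratios across the rows are to be taken as a sign that the ratio does not depend on dose.

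Neither document floors the MED at zero, defines it as 0 when placebo alone reaches -0.5 g/dL, or says how negative draws are to be reported.

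**The concern.** The definition and the formula disagree when E0 is above -0.5. By definition, the smallest dose that reaches the target is then 0 mg. The formula instead runs the Emax curve backwards and returns a dose below zero, outside the SAP's own dose range.

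This is not a remote corner of the parameter space, because the MED target sits close to where the plan expects the placebo response to be. Two outputs are at stake. The first is the lower credible limit of the MED, one of the listed dose-response inferences. The second is the dose ratio at -0.5 g/dL, where a negative or near-zero dose can sit above or below the line. That row feeds the check on whether one conversion ratio serves all doses.

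**Working it through.** **Inputs.** Primary priors (Protocol 9.4.1.1, Table 6; SAP 7.1.2): E0 Normal with mean -0.67 and SD 0.146; Emax Normal with mean 5.26 and SD 1.337; ED50 uniform from 10 to 120; precision Gamma(1,1). Planning values (Protocol 9.2.1): E0 = -0.666, Emax = 5.258, SD 1 g/dL, 75 subjects (15 in each of 5 arms), ED50 = 37.28 or 78 mg.

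**1. The plan's own figures.** The delta method on the stated Emax model, with 15 per arm at 0, 10, 15, 25 and 30 mg, gives 95% half-widths of 2.84 and 5.33 for MED and 2.85 and 5.93 for TD. Protocol Table 4 prints 2.85, 5.34, 2.86 and 5.94, so the model is being read as intended. The planning MEDs are 37.28 x 0.166/5.758 = 1.07 mg and 78 x 0.166/5.758 = 2.25 mg, both smaller than their half-widths.

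**2. When MED is negative.** Under the primary prior, Emax exceeds -0.5 by (5.26 + 0.5)/1.337 = 4.3 SD, so the denominator is positive in practically every draw. MED is therefore below 0 exactly when E0 > -0.5, and the lower 95% limit is below 0 when the posterior P(E0 > -0.5) exceeds 2.5%.

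- Primary prior: 1 - Phi((-0.5 + 0.67)/0.146) = 1 - Phi(1.164) = 12.2%.
- Weaker sensitivity prior (mean -1.2, SD 1): 1 - Phi(0.70) = 24.2%.

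**3. How often the lower limit is negative.** Posterior computed on a grid over ED50 and variance, bivariate normal for E0 and Emax given those; primary priors, SD 1, 15 per arm, 1,500 simulated trials per setting:

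| True E0 (g/dL) | ED50 37.28 | ED50 78 |
|---|---|---|
| -0.666 (planning value) | 92% | 88% |
| -0.72 (earlier placebo mean, Protocol 4.4) | 90% | 81% |
| -0.90 (assumed) | 70% | 46% |
| -1.0 (assumed) | 51% | 24% |
| -1.2 (centre of the SAP's QD and weaker E0 priors) | 21% | 4% |

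With the truth drawn from the primary priors, the rate is 81% at SD 1, 70% at SD 0.8 (assumed) and 91% at SD 1.5.

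**4. Effect of a floor on MED.** For data lying exactly at the planning values, the 95% interval changes from (-0.72, 2.49) to (0, 2.49) mg at ED50 37.28, with the median 1.02 either way. At ED50 78 it changes from (-1.22, 4.93) to (0, 4.93), with the median 2.18 either way. P(TD < 0) is about 0 under the primary priors and at most 0.5% under the weaker ones.

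**5. The dose ratio at -0.5 g/dL.** The documents do not give the QD posterior. As an assumption, I took QD E0 and Emax as independent draws from the TIW priors, which the SAP says come from the QD study, and set the QD ED50 to the TIW planning value divided by 2.33. The true ratio is then 2.33 at every response. The QD dose in the denominator is 16 x 0.166/5.758 = 0.46 mg for the first ED50. The E0 SD alone contributes about 16 x 0.146/5.758 = 0.41 mg to its spread, so it passes through zero in about 12% of draws. Across both ED50 settings:

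| Response | Median ratio | 95% limits | Negative draws |
|---|---|---|---|
| -0.5 g/dL | about 1.5 | about -19 to +23 | about 20% |
| 0 g/dL | about 2.3 | about 1.0 to 5.0 | about 0 |

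At +0.25 and +0.5 g/dL the median is about 2.3, with limits of about 1.0 to 4.4.

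**The case against.** The case for leaving the plan alone has real substance. A floor is a monotone transformation, so each floored percentile is just the larger of 0 and the reported one, and a reader can make that correction unaided. The median is unchanged as long as P(E0 > -0.5) stays below one half. The posterior of E0 is already tabulated and plotted, which largely shows whether placebo alone reaches -0.5. On the ratio, the SAP calls its response values possible choices, produces these tables only where the models are appropriate, prefers the linear model where it fits well, and bases conversion on the totality of approaches.

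Most of this stands for the MED itself and keeps the point modest. It does not cover the ratio row. No reader can repair a ratio whose denominator changes sign, and the plan gives no instruction to set that row aside when judging similarity.

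Several stronger readings are tempting but not supported:

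- A reader might infer that a negative lower limit is all but certain. It depends on the true placebo change, and at -1.2 g/dL it is uncommon.
- A reader might infer that the reported MED is biased downward through its mean. The mean is not a planned MED summary, and at the planning values it would move only from 0.99 to 1.04 mg or from 2.09 to 2.18 mg.
- A reader might infer that Protocol Table 4 prints impossible limits. It prints half-widths only, as a planning measure of precision, so there is nothing there to restate.
- A reader might extend the point to the -0.25 g/dL dose. Under the primary prior P(E0 > -0.25) is about 0.2%, so a floor there changes almost nothing.

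**Conclusion.** The point holds as a gap in an analysis rule. The draw-level formula does not match the stated definition when E0 exceeds -0.5, and nothing in either document covers that case. With a true placebo change of about -0.67 to -0.72 g/dL, SD 1 and 15 per arm, the reported lower MED limit falls below 0 mg in about 80-90% of trials; at -1.2 g/dL the figure is about 4-21%. The damage to the MED is confined to that limit.

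The more consequential effect is on the -0.5 g/dL dose ratio. There a constant true ratio of 2.33 can appear as about 1.5, with limits too wide to use, beside about 2.3 at the higher responses. That could be misread as dose dependence. The size of this second effect rests on the assumed QD posterior; the mechanism, a denominator that can cross zero, does not. The other dose-ratio rows considered and the target dose are not called into question.

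**What to change.** - Track MED = max(0, ED50 x (-0.5 - E0)/(Emax + 0.5)) in PROC MCMC. Report the posterior P(E0 >= -0.5) beside the MED median and 95% interval.
- Leave the -0.5 g/dL row out of the dose-ratio table and out of the similarity check unless both the TIW and the QD dose are positive in at least 97.5% of draws. A floor does not rescue this ratio, because the denominator then becomes 0.

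The cost is one line of code, one extra reported probability and one sentence on the ratio row, with no effect on data collection or patients. The downside is that the -0.5 g/dL row will probably not be reported: at the planning values only about 86-88% of TIW draws are positive on average (100% minus the 13.6% and 11.8% mean posterior probabilities of a negative MED).

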7.1.2. Planned Hgb Efficacy Statistical Analyses

Primary Statistical Analyses
Endpoint(s)

 • Hgb change from baseline at Day 29
Model Specification

 • The primary endpoint is change in Hgb from baseline at Day 29. To model the dose-response relationship a three-parameter Emax model is planned, where Emax is assumed an appropriate model based on the biology and QD-dose-response modeling completed to date for GSK1278863. 
This model assumes the following form:
 $\Delta Hgb = E0 + \frac{(Emax - E0)}{1 + \left(\frac{ED50}{dose}\right)} + \epsilon$ 
Where:
 
 • ΔHgb is the change in Hgb from baseline at Day 29 • E0 is the placebo response • Emax is the maximum response

Primary Statistical Analyses											

 ED50 is the dose that attains the intermediate response, i.e. where $(E_0 + E_{max}) / 2$, is attained ϵ is a random error assumed to be normally distributed with mean zero and constant variance (σ^2) 
The observed change in Hgb from baseline at Day 29 will be used as the response variable in the Emax model. Subjects who have a Day 15 Hgb measurement but a missing Day 29 Hgb measurement will be included with a Day 29 value imputed (see Section 11.7.2.1). Any subject who prematurely discontinues dosing prior to Day 15 will be non-evaluable for the dose-response analysis.
											
Prior Distribution											

The Emax model will be fitted using Bayesian statistical methods (i.e. a posterior Emax model). Prior distributions for each of the model parameters have been based on the estimates obtained from GSK study PHI113633. This modeling provides confidence in setting prior distributions for E0, however, there is greater uncertainty in the estimation of Emax and ED50, which will be explored in sensitivity analyses with alternative (weaker) prior distributions.
											

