
Prior Distributions of the Primary Model
 
  
 Emax Model Parameters	Bayesian Priors	
   
 E0	~Normal (-0.67, (0.146)²)	
 
 Emax	~Normal (5.26, (1.337)²)	
 
 ED50	~Uniform (10, 120)	
 
 Tau (1/σ^2)	~Gamma (1,1)	
  
		Emax Model Parameters	Bayesian Priors	E0	~Normal (-0.67, (0.146) ²)	Emax	~Normal (5.26, (1.337) ²)	ED50	~Uniform (10, 120)	Tau (1/ σ^2)	~Gamma (1,1)
Emax Model Parameters	Bayesian Priors										
E0	~Normal (-0.67, (0.146) ²)										
Emax	~Normal (5.26, (1.337) ²)										
ED50	~Uniform (10, 120)										
Tau (1/ σ^2)	~Gamma (1,1)										
Model Fitting in SAS											

The model will be fitted in SAS using the MCMC procedure.
 
 Blocking: Sampling blocks of parameters instead of the parameters separately may speed up the convergence to the target distribution. Blocks are specified in the PARMS statement. Seed: The seed for reproducibility of results will be set to 123. 											
Starting Values											

In order to check the validity of the Emax model fit, five separate Monte Carlo Markov Chain's chains will be fitted each with the following starting points:
 
 Chain 1) E0 = -1.2, Emax = 5.5, ED₅₀ = 50, var = 1 Chain 2) E0 = -0.75, Emax = 7, ED₅₀ = 22.5, var = 2 Chain 3) E0 = -1.65, Emax = 4, ED₅₀ = 80, var = 0.5 											

Primary Statistical Analyses
 
 ▪ Chain 4) $E_0 = -1.65$, $E_{max} = 7$, $ED_{50} = 22.5$, $var = 1$ ▪ Chain 5) $E_0 = -0.75$, $E_{max} = 4$, $ED_{50} = 100$, $var = 2$ 
When the starting values are taken in an area where the posterior probability is low, it may take a long time to escape from the starting positions and mixing could be low initially. In this case, other starting values could be tried.

Burn In
 
“Burn-in” is the portion of the chain where convergence has not yet been achieved. “Discarding burn-in” is the practice of discarding the initial portion of a Markov chain. This will be set to 5000 iterations.

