
Dose ratio between TIW and QD doses that produce the same Hgb response will be estimated by different approaches. The dose ratio that will be used to make an informative decision about conversion of QD initial and maintenance dose regimens to three-times weekly doses/regimens will be based on the totality of the data obtained from different approaches.
 
 The TIW dose response estimations will be obtained from the above fitted models. In addition, the QD dose response estimations will also be obtained by fitting the same models as described above (two Emax models and a linear model) using GSK study PHI113633 data excluding Japan. The prior information and the starting values for the QD Bayesian Emax model is shown below: 
Five separate Monte Carlo Markov Chain's chains will be fitted each with the following starting points:
 
 Chain 1) $E0 = -1.2, Emax = 5.5, ED_{50} = 16, var = 1$ Chain 2) $E0 = -0.75, Emax = 7, ED_{50} = 22.5, var = 2$ Chain 3) $E0 = -1.65, Emax = 4, ED_{50} = 9.5, var = 0.5$ Chain 4) $E0 = -1.65, Emax = 7, ED_{50} = 22.5, var = 1$ Chain 5) $E0 = -0.75, Emax = 4, ED_{50} = 9.5, var = 2$ 
Prior Distributions for QD Bayesian Emax Model
 
  
 Emax Model Parameters	Bayesian Priors	
   
 E0	$\sim \text{Normal}(-1.2, (0.45)^2)$	
 
 Emax	$\sim \text{Normal}(5.5, (1.5)^2)$	
 
 ED50	$\sim \text{Uniform}(5, 50)$	
 
 Tau ($1/\sigma^2$)	$\sim \text{Gamma}(1, 1)$	
  
		Emax Model Parameters	Bayesian Priors	E0	$\sim \text{Normal}(-1.2, (0.45)^2)$	Emax	$\sim \text{Normal}(5.5, (1.5)^2)$	ED50	$\sim \text{Uniform}(5, 50)$	Tau ($1/\sigma^2$)	$\sim \text{Gamma}(1, 1)$
Emax Model Parameters	Bayesian Priors										
E0	$\sim \text{Normal}(-1.2, (0.45)^2)$										
Emax	$\sim \text{Normal}(5.5, (1.5)^2)$										
ED50	$\sim \text{Uniform}(5, 50)$										
Tau ($1/\sigma^2$)	$\sim \text{Gamma}(1, 1)$										

Primary Statistical Analyses

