- Although the Emax models and the linear model will be explored to estimate the dose ratio between the TIW and the QD doses, the linear model will be more reliable if it is well-fitted across the TIW and the QD dose range. This is because the QD and TIW dose ranges are expected to only cover the beginning part of the Emax curves. Therefore if any doses lie outside the dose ranges (such as ED50), they will be poorly estimated.
- The 95% bootstrap CI of the estimated dose ratios can be constructed based on the 2.5 percentile and the 97.5 percentile of 1000 bootstrap simulations (Efron and

Primary Statistical Analyses
 
Tibshirani, 1993).
 
 For Bayesian Emax models, the posterior distributions of the estimated doses will be obtained by the PROC MCMC procedure to estimate the dose ratios, of which the 95% Bayesian credibility intervals can be constructed based on the 2.5 percentile and the 97.5 percentile of the 500,000 estimations.

Model Checking & Diagnostics
 
 Refer to Convergence Diagnostics and Posterior Estimates

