2.7.	Per-Protocol	Table 7.012	Sensitivity Summary of Posterior Estimates from the Bayesian 3 Parameter Emax Dose-Response Model for Change in Hemoglobin at Day 29	
Same as template 7.010, just based on different pop
 
Based on both observed on-treatment Hgb and imputed Hgb at Day 29 visit. If Day 29 Hgb is imputed using Day 15 Hgb, Day 15 Hgb must be measured on-treatment.
 
Will be performed by GSK

2.8.	ITT	Linear_DR	Dose-Response Linear Model for Change in Hemoglobin at Day 29	
Based on both observed on-treatment Hgb and imputed Hgb at Day 29 visit. If Day 29 Hgb is imputed using Day 15 Hgb, Day 15 Hgb must be measured on-treatment.
 
Will be performed by GSK

2.9.	Completers	Linear_DR	Dose-Response Linear Model for Change in Hemoglobin at Day 29	
Based on observed on-treatment Hgb at Day 29 visit.
 
Will be performed by GSK

2.10.	Per Protocol	Linear_DR	Dose-Response Linear Model for Change in Hemoglobin at Day 29	
Based on both observed on-treatment Hgb and imputed Hgb at Day 29 visit. If Day 29 Hgb is imputed using Day 15 Hgb, Day 15 Hgb must be measured on-treatment.
 
Will be performed by GSK

2.11.	ITT	Dose_Ratio_1	Summary of Dose Ratio Between Three-Times Weekly Doses (Observed) and QD Doses (Estimated by Bayesian Emax Model)	
Will be performed by GSK when the dose-response model is appropriate

Efficacy: Tables				
No.	Population	IDSL / TST ID / Example Shell	Title	Programming Notes
2.12.	ITT	Dose_Ratio_1	Summary of Dose Ratio Between Three-Times Weekly Doses (Observed) and QD Doses (Estimated by Frequentist Emax Model)	Will be performed by GSK when the dose-response model is appropriate
2.13.	ITT	Dose_Ratio_1	Summary of Dose Ratio Between Three-Times Weekly Doses (Observed) and QD Doses (Estimated by Linear Model)	Will be performed by GSK when the dose-response model is appropriate
2.14.	ITT	Dose_Ratio_2	Summary of Dose Ratio Between Three-Times Weekly Doses (Estimated by Bayesian Emax Model) and QD Doses (Estimated by Bayesian Emax Model) at Selected Hgb Responses	Will be performed by GSK when the dose-response models are appropriate
2.15.	ITT	Dose_Ratio_2	Summary of Dose Ratio Between Three-Times Weekly Doses (Estimated by Bayesian Emax Model) and QD Doses (Estimated by Frequentist Emax Model) at Selected Hgb Responses	Will be performed by GSK when the dose-response models are appropriate

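### Table 2.11: as written, the Bayesian 95% interval for the read-off dose ratio treats the observed three-times-weekly arm mean as known, so it is too narrow (coverage roughly 40-70%, depending on assumptions)

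*SAP*

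**What the plan says.** SAP 7.1.2 (Dose Ratio Estimation) describes several routes to the ratio. In the read-off route, each TIW arm's observed mean Day 29 change is put into a QD dose-response model: "Using the observed mean Hgb response values as a bridge, the corresponding QD doses will be estimated using Emax models or a linear model". The TIW dose divided by that QD dose is the ratio, tabulated with a bootstrap or Bayesian 95% interval.

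The QD models are fitted "using GSK study PHI113633 data excluding Japan". For the Bayesian version, "the posterior distributions of the estimated doses will be obtained by the PROC MCMC procedure to estimate the dose ratios", with limits at the 2.5 and 97.5 percentiles of the 500,000 draws. For the bootstrap version the SAP specifies 1000 replicates with percentile limits and does not say which study's subjects are resampled.

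SAP 11.14.6 titles Table 2.11 "Summary of Dose Ratio Between Three-Times Weekly Doses (Observed) and QD Doses (Estimated by Bayesian Emax Model". Tables 2.12 and 2.13 are the frequentist Emax and linear counterparts.

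The only inversion of the Emax curve that the SAP writes out is the one for the minimally effective and target doses, where "a variable in the PROC MCMC code will be tracked with the MCMC algorithm and calculated as follows" with the Hgb change entered as a fixed number.

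**The concern.** A ratio read off this way has two sources of error: the fitted QD curve and the TIW arm mean put into it. In Table 2.11 the TIW side is labelled as observed, and the only posterior available is that of a curve fitted to another study. That posterior contains no TIW data. Percentiles of QD doses computed from it at a fixed observed mean therefore describe the curve's uncertainty alone.

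The SAP asks whether the ratios are fairly similar across doses, and it feeds this table, with the other methods, into the overall judgement on converting QD to TIW regimens. A reader of the table would credit a single arm of about 15 subjects with precision that it does not have.

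**Working it through.** **Plan's own precision figures.** The documents give no precision for the dose ratio. The nearest figures are in Protocol Table 4. The delta method on the three-parameter Emax model (15 per arm at 0, 10, 15, 25 and 30 mg, SD 1) gives half-widths of 2.85 and 5.93 for the target dose and 2.84 and 5.33 for the minimally effective dose. Table 4 prints 2.86, 5.94, 2.85 and 5.34. The model and inputs used here are therefore the plan's.

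**Inputs**
- Protocol 4.3: about 15 evaluable subjects per arm.
- Protocol 9.2.1: SD 1 g/dL; "E0 = -0.666 and Emax = 5.258 (estimates based on PHI113633 Emax model"; QD ED50 33.41 mg; theoretical ratio 2.33.
- SAP 7.1.2, QD priors: E0 N(-1.2, 0.45²), Emax N(5.5, 1.5²), ED50 U(5, 50), tau Gamma(1, 1).
- Precision of PHI113633: "Prior distributions for each of the model parameters have been based on the estimates obtained from GSK study PHI113633". The E0 prior has mean -0.67 and SD 0.146, so 0.146 is read as that study's SD for E0 (an assumption).
- Assumed: true constant ratio 2.33; equal QD arms at 0, 4, 6, 10 and 12 mg. Protocol 4.5 names the four active doses; arm sizes and the full arm list are not given.

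**Step 1: the two errors.** SE of a TIW arm mean = 1/√15 = 0.258 g/dL. Under the SAP's QD priors, about 30 per QD arm reproduces SD(E0) = 0.146. The curve SD, s, at the four read-off points is then 0.085, 0.084, 0.110 and 0.128 g/dL. The share of variance left out is (1/15)/(1/15 + s²). At s = 0.085 this is 0.0667/0.0739 = 90%; at s = 0.128 it is 0.0667/0.0831 = 80%.

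**Step 2: coverage.** The curve is monotone. The as-written interval therefore contains the true QD dose exactly when the observed TIW mean falls inside the curve's 95% band at that dose:

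coverage = 2Φ(1.96·s/√(s² + 1/15)) - 1

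| TIW dose | True QD dose (mg) | s | Coverage |
|---|---|---|---|
| 10 mg | 4.29 | 0.085 | 46% |
| 15 mg | 6.44 | 0.084 | 45-46% |
| 25 mg | 10.73 | 0.110 | 56% |
| 30 mg | 12.88 | 0.128 | 62% |

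Simulation of the full posterior at about 30 per arm gives 46-64% on the QD-dose scale. Drawing the TIW mean as well brings coverage to about 95%.

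**Step 3: sensitivity**
- Other QD arm sets held at SD(E0) = 0.146, with or without the QD priors: 42-72%.
- 20 to 40 per QD arm: 41-69%.
- 10 per QD arm: 68-79%. 60 per QD arm: 36-51%.
- 18 per TIW arm: 47-65%.
- SD 1.5 with SD(E0) held at 0.146: 35-44%.
- If s were 0.146 at every dose: 1.96 × 0.146/√(0.0213 + 0.0667) = 0.965, coverage 67%. This is a check and not a ceiling, because s can exceed 0.146 in sparser designs.

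**Step 4: scale.** On the ratio scale the simulated 10 mg figure is 52%, against 46% on the QD-dose scale. The gap comes from draws in which the QD dose crosses zero and the ratio changes sign, so the QD-dose scale is the one to quote.

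**Step 5: one row.** For 25 mg on expected data the ratio is 2.33. The interval is 1.88 to 2.79 as written and 1.39 to 4.31 with both errors.

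**Bootstrap, conditional.** For Table 2.13 at 20 to 40 per QD arm, coverage is 37-72% if the TIW arm is not resampled. At 30 per arm it is 92-94% if it is.

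**The case against.** The strongest reply is that the SAP never says the TIW mean is held fixed. The constant-response inversion is written for the minimally effective and target doses in this study and not for Table 2.11, and the interval wording is permissive. The mock shells in Appendix 15 are not in the text available here, so a note there on the interval cannot be excluded. This tempers certainty about what the programmers would do. It does not supply a propagation step: the curve's data source, the observed label on the TIW side and the stated source of the interval together leave the TIW error out of a literal run.

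A second reply is that little hangs on these intervals, and this largely stands. The SAP's tests of dose dependence use the similarity of the point ratios and the size of an intercept. The protocol (9.4.1.2) presents read-off as producing point estimates, several methods are combined, and TIW arm means with 95% CIs appear in Figures 2.2 and 2.16.

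Three stronger readings are tempting and are not supported.
- A reader might infer that the prior table fixes coverage at one narrow range. It gives no ED50 precision, covariance, sample size or arm list, and does not say whether its estimates excluded Japan. The calibration also gives an Emax SD of about 1.2 against the stated 1.337.
- A reader might infer that Tables 2.12-2.13 are wrong. Resampling both studies is compatible with the text.
- A reader might infer that the equal-response Tables 2.14-2.22 share the fault, or that the SAP judges ratios by interval overlap or against 2.33 using these intervals. In those tables both curves are fitted, and no such rule is written.

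**Conclusion.** The point holds for the Bayesian interval in Table 2.11 as written. It omits the larger of two error components, and its coverage is roughly 40-70% where 95% is claimed. That range rests on SD 1, about 15 per TIW arm, a constant true ratio, and PHI113633 designs broadly consistent with an E0 SD of 0.146. More extreme assumptions move it to 35-79%; none of those examined comes near 95%.

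Tables 2.12-2.13 need only a clarification. The point estimates, the equal-response tables and the rules based on point ratios are untouched. The effect on the conversion decision is modest, but a planned table should not carry a mislabelled interval when the remedy is this small. It should be fixed.

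**What to change.** Add to the interval text in SAP 7.1.2:
- For Table 2.11, each MCMC draw also draws the TIW arm mean from its sampling or posterior distribution (for example, t with n - 1 df, centred at the arm mean with scale s/√n, where s here is the arm's SD), independently of the QD curve. The QD dose, ratio and percentiles are computed after that.
- For Tables 2.12-2.13, the bootstrap resamples both studies within arm.
- Where the QD-dose interval reaches 0, the QD-dose interval is shown and the ratio is marked as unbounded.

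The cost is a short SAP addition and about one line in each read-off program, with no new data and no change to the point estimates. The downside is visible in the output. QD-dose intervals become about 2 to 4 times wider; from Step 1, √(s² + 1/15)/s runs from 2.3 at s = 0.128 to 3.2 at s = 0.084. The 10 mg row would have no bounded ratio in about a third of trials under the Bayesian Emax model, and in 55-61% under the linear bootstrap. That is the real uncertainty of a 15-subject arm, which the present interval would hide.
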